### **Cessation Study**

After the in-person baseline session, participants assigned to the Modern Usual Care (M-UC) will have no other treatment visits or calls, other than the single call from the Wisconsin Tobacco Quit Line. However, participants in this condition will receive the 6 assessment calls at Weeks 4, 8, 16, 26, 39 and 52.

Participants in the Abstinence-Optimized Cessation Treatment (AOCT) will attend three additional visits at 1 week pre-quit, on the Target Quit day (TQD), and 1 week post-quit, during which they will receive the in-person counseling (see Table 5). In addition, AOCT participants will receive 8 counseling calls at Weeks 3, 4, 6, 8, 10, 14, 18, and 22 as well as 7 or 11 automated calls that encourage medication adherence at Days 1, 3, 10, 17, 24, 31 and 45 (those who are still smoking at Week 8 will receive 4 additional automated adherence calls to encourage medication use at Days 73, 101, 126 and 154). Participants in AOCT will receive 3 weeks of pre-quit nicotine mini-lozenges at Visit 1 and will receive nicotine mini-lozenges and

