**Cessation Study**

Modern Usual Care (M-UC). We developed the Modern Usual Care (M-UC) to serve as a control condition to demonstrate that the abstinence-optimized cessation treatment would result in improved cessation compared to what would typically happen in a primary care practice. However, we wanted a control condition that was sufficiently effective to serve as a reasonable control condition. Therefore, while “usual care” in primary care may not extend beyond advice to quit smoking, participants assigned to the M-UC will receive 8 weeks of nicotine patch, a single brief, in-person counseling session, a faxed referral to the Wisconsin Tobacco Quit Line (WTQL), and will be signed up for either the QUITNOW app or the Web Coach (both provided by Alere Wellbeing, the vendor that provides the WTQL services).

*Medication.* M-UC participants will receive 8 weeks of nicotine patch (participants who smoke >10 cigs/day: 4 weeks of 21 mg, 2 weeks of 14 mg, and 2 weeks of 7 mg nicotine patches; participants who smoke ≤10 cigs/day: 6 weeks of 14 mg and 2 weeks of 7 mg nicotine patches) at their first clinic visit and will be instructed to begin using the patch on the TQD. All participants will be given complete instructions on proper patch use, including an information sheet and contact information if they want to ask questions regarding their medication, and/or symptoms they experience. We will recommend dosage/use alterations as per good clinical practice if the participant experiences any medication side effects. The case manager will refer participants to their primary care physician should they require medical consultation. Participants will be asked to take the medication for the full 8 weeks, regardless of whether they return to smoking.

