*Counseling and Technology.* Participants in the M-UC condition will receive a brief (10 minute) counseling session that will involve setting a quit date, identifying motivation for quitting and preparing for the quit date. Participants will then complete a fax-to-quit referral form for the WTQL, which will be faxed to the WTQL and result in the WTQL calling the participant to provide cessation counseling at the time of the participant’s choosing. Finally, the health counselor and the participant will review a handout that educates the participant about the QUITNOW app and the Web Coach feature from the WTQL. The handout will review how the app will provide access to evidence-based tools to help the smoker quit and for the first 2 weeks post-quit will provide active support and how to complete the 3 set-up screens for the app: 1) entering the quit date; 2) entering the number of cigs/day they smoke and the cost/pack; and 3) entering the reasons for quitting. The handout will also remind participants to mention their interest in the Web Coach feature to the Quit Line caller, who will then send them the link and password so that they can access the Web Coach after their Quit Line call. The handout will also provide the link to a brief 4-minute video about the Web Coach site, which will illustrate how they can enter their quit date and medication into their quit plan and access the different tools and support from the website through quit coaches or other quitters in the web community.

Abstinence-Optimized Cessation Treatment (AOCT). In our prior research using the Phase-Based Model and MOST, we conducted two screening experiments and experimentally

“Breaking Addiction to Tobacco for Health (BREATHE) Study”

PI: [name], MPH, MBA; UW-CTRI Center Grant: 1P01CA180945-01.

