*Counseling and Automated Calls.* Participants in the AOCT will receive In-Person Cessation Counseling which will be supportive and focus on skill development and problem-solving, as recommended by the 2008 PHS Guideline. The goals of Cessation-phase counseling are to prepare for the TQD (e.g., reinforce motivation, remove cigarettes and smoking paraphernalia from the environment, plan for the quit day), develop techniques to cope with withdrawal symptoms and smoking triggers, including negative affect and withdrawal, and provide support. There will be three 20-min In-person Cessation Counseling sessions (Week -1, TQD, Week 1). The timing and counseling content of the three sessions is consistent with the 2008 PHS Guideline recommendations. AOCT participants will also receive 8 Maintenance-phase smoking cessation counseling sessions. These 15-minute calls emphasize content similar to that provided in the In-Person counseling, namely support and problem-solving.

Finally, participants will receive 11 brief, automated calls reminding them to use their medications properly at Days 1, 3, 10, 17, 24, 31, 45, 73, 101, 129, and 157. However, if participants report that they are not smoking during the Week 8 assessment call, they will not receive any further automated adherence messages (i.e., they would get 7 automated calls during the first 6 weeks of their quit attempt). This decision was based on data from our prior study that suggested that smokers who were able to achieve abstinence early in the quit attempt, appeared to have less long-term cessation success if they got the automated adherence calls.

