**Cessation Study**

*Primary Aim 1:* A primary aim of Project 3 is to compare Abstinence-Optimized Cessation Treatment (AOCT) with Modern Usual Care (M-UC) on 7-day point-prevalence abstinence evaluated at 8, 16, 26, 39 and 52 weeks postquit. We will use GLMM implemented via SAS PROC GLIMMIX (SAS Institute Inc., Cary, North Carolina) to test the group effects in longitudinal models. Specifically, we hypothesize that participants receiving AOCT will have higher cessation rates at each timepoint than those receiving M-UC. We will also analyze other clinical outcomes because they provide complementary information about outcome (e.g., initial cessation, 6- and 12- month point-prevalence abstinence, latency to lapse and relapse, and treatment engagement and adherence) as recommended by SRNT Workgroup and others. We will evaluate initial cessation (did or did not establish 24 hours of abstinence in the first 2 weeks

“Breaking Addiction to Tobacco for Health (BREATHE) Study”

PI: [name], MPH, MBA; UW-CTRI Center Grant: 1P01CA180945-01.

following the quit day) and 6- and 12-month abstinence rates using logistic regression and latency to lapse and relapse using Cox proportional-hazards regression. We will also examine cessation outcomes controlling for treatment adherence in secondary analyses. The distributions of the adherence data (percentage of days using nicotine replacement; number of mini-lozenges used per day; percentage of counseling sessions completed) will be examined to inform decisions about transformation and analysis options.

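### The Cessation Study's secondary analysis controlling for adherence adjusts the arm comparison for a post-randomisation measure that is not comparable between arms, so the adjusted effect can be biased in either direction.

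*Combined protocol and SAP*

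**What the plan says.** In Analytic Plans, Cessation Study, Primary Aim 1, the primary comparison of Abstinence-Optimized Cessation Treatment (AOCT) with M-UC is a longitudinal mixed model for 7-day point-prevalence abstinence, with no adherence term mentioned. The plan then adds: "We will also examine cessation outcomes controlling for treatment adherence in secondary analyses". The adherence data are listed as "percentage of days using nicotine replacement; number of mini-lozenges used per day; percentage of counseling sessions completed". Decisions on transformation and analysis wait until the distributions have been seen. No estimand, model, arm-specific definition or denominator is given.

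The Intervention Components section describes the M-UC package as "8 weeks of nicotine patch, a single brief, in-person counseling session", plus a faxed Quit Line referral and an app or web programme. No lozenge is listed for M-UC. Study Procedures says that after baseline these participants "will have no other treatment visits or calls, other than the single call from the Wisconsin Tobacco Quit Line".

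AOCT has three in-person sessions and eight maintenance calls. It supplies lozenges for three weeks before quitting, then patch and lozenge for 26 weeks after it, with encouragement to average 9 lozenges a day.

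**The concern.** A model of abstinence on arm plus adherence estimates the arm effect at a common value of adherence. Where a measure takes only one value in M-UC, that value is the only point at which the arms overlap. With lozenges it is 0, so the arm term sets AOCT non-users against all of M-UC. With sessions at 100%, it sets AOCT full attenders against all of M-UC. AOCT non-users are likely to be less motivated than average and full attenders more so, while the M-UC group is unselected. Randomisation no longer protects either comparison.

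The design makes a link between adherence and abstinence more likely: automated adherence calls stop for AOCT participants who report not smoking at Week 8, a time point that is itself an outcome. At stake is a secondary estimate whose direction could depend on which adherence measure is entered.

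**Working it through.** **The plan's own figure.** The power section gives .80 for 20% against 30% abstinence at 6 months, with 300 per arm and alpha .05 (two-sided assumed). The null standard error is √(0.25 × 0.75 × 2/300) = 0.0354, and the alternative is √((0.20 × 0.80 + 0.30 × 0.70)/300) = 0.0351. Power = Φ[(0.10 − 1.96 × 0.0354)/0.0351] = 0.81. The stated figure reproduces. It concerns the unadjusted contrast, which this point does not dispute.

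**The measures by arm, from the documents.**

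| Measure | M-UC | AOCT |
|---|---|---|
| Lozenges per day (study supply) | 0 for all | varies; encouraged to average 9 |
| Counselling sessions | 1, or 2 with the Quit Line call | 3 + 8 = 11 |
| Days on nicotine replacement | varies, over 8 weeks | varies, over 26 weeks, plus 3 pre-quit weeks of lozenge |

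If the Quit Line call counts, an M-UC participant who had the study session can score only 50% or 100%. If nicotine replacement days were taken over a common 26 weeks, full use of the M-UC supply would score 8/26 = 31%.

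**Simulation 1: large sample (400,000, half per arm).** The confounding and adherence distributions are assumptions. An unmeasured factor U, standard normal, raises the log-odds of abstinence by 0.8 per unit. Abstinence is set at 20% in M-UC and at 20% or 30% in AOCT. Latent adherence is L = kU + standard normal noise, with k = 0.5 (moderate) or 1.0 (strong). AOCT lozenges are 5 + 2.5L, held within 0 to 12. AOCT session completion is expit(0.8 + L), rounded to elevenths, a mean of about 65%. M-UC is fixed at 0 lozenges and 100% of sessions. Nicotine replacement days vary in both arms. Each model is a logistic regression of abstinence on arm and one measure.

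| Adjusted for | Arm OR, no true effect (k = 0.5 to 1.0) | Arm OR, 20% v 30% |
|---|---|---|
| Nothing | 1.0 | 1.7 |
| Lozenges per day | 0.53 to 0.40 | 0.93 to 0.72 |
| % sessions (M-UC at 100%) | 1.7 to 2.0 | 2.9 to 3.5 |
| % nicotine replacement days, equal means | 1.00 | 1.75 to 1.77 |
| Same, AOCT mean lower (about 0.45 v 0.63) | 1.3 to 1.4 | 2.3 to 2.6 |
| Same, AOCT mean higher (about 0.63 v 0.45) | 0.75 to 0.69 | 1.3 to 1.2 |

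With k = 0, so that U does not affect adherence, each single-measure model returns the unadjusted odds ratio.

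**Simulation 2: trials of 300 per arm, no true effect.** Abstinence is about 19%. Motivation acts on abstinence with log-odds slope 0.8 (8% v 33% abstinent in the lowest and highest thirds) or 0.4 (11% v 24%), and on the adherence probability p with slope 0.8. AOCT sessions are binomial(11, p)/11, mean about 63%; AOCT lozenges are Poisson(7p).

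| Adjusted for | Stronger link: OR (significant) | Weaker link: OR (significant) |
|---|---|---|
| % sessions, Quit Line call not counted | 2.4 to 2.6 (80 to 85%) | 1.6 to 1.7 (35%) |
| % sessions, call counted as a second M-UC session | 1.4 (34 to 36%) | 1.2 (12 to 12.5%) |
| Lozenges per day | 0.53 to 0.54 (40%) | 0.72 to 0.73 (13 to 14%) |

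Ranges within a cell are results from separate runs. The unadjusted odds ratio is 1.0 throughout.

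**The case against.** A reader might infer that all three measures are fixed by design in M-UC. The documents do not support that. M-UC patch use is up to the participant: "Participants will be asked to take the medication for the full 8 weeks, regardless of whether they return to smoking". Nicotine replacement use is assessed at each contact, and the adherence items in Table 12 are not restricted to AOCT. That measure varies in both arms and gave essentially no bias in the simulations when mean adherence was equal.

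Session completion is not necessarily 100% in M-UC either. The protocol describes the Quit Line call as cessation counselling and names it as the exception to no further treatment contact. It can be missed. Counting it roughly halves the false-positive rate under the stronger link, although bias remains.

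It is also fair that the plan commits to no particular model and defers analytic choices until the distributions are examined, when a covariate constant in one arm would be noticed. But noticing it would not settle what the adjusted effect means, and the plan has no rule for that case. Finally, the analysis is labelled secondary, and the confounding strengths are assumed. These objections limit the size and certainty of the point but do not remove the defect.

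**Conclusion.** The concern holds in limited form. The planned analysis conditions on a post-randomisation variable with different scales by arm, so its arm effect can be biased in either direction depending on the measure. With no true effect, the simulations give odds ratios of about 0.4 to 0.7 for lozenges, 1.6 to 2.6 for sessions (1.2 to 1.4 with the Quit Line call counted) and 1.0 for nicotine replacement days at equal means. At the planned 20% against 30%, lozenge adjustment turns an odds ratio of about 1.7 into 0.93 to 0.72, which reverses the direction.

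This requires a common cause of adherence and abstinence, or smoking status acting on adherence. The documents give no figure for its strength, so the sizes are illustrations. It would go too far to say that the adjusted effect must be biased, or that the primary result is compromised: the primary model is not described as adherence-adjusted, and the power statement stands.

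**What to change.** In Primary Aim 1, state that the unadjusted randomised contrast is the treatment effect, and drop any arm effect adjusted for adherence. In its place:

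- Report lozenge use and session completion, and their association with abstinence, within AOCT only.
- Report nicotine replacement days within each arm over that arm's own supply period, stating whether the AOCT pre-quit weeks count.
- Label these associations as non-causal.
- If an effect among those who received treatment is wanted, name the estimand and state its assumptions.

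For that last item, receipt should not be defined as at least one AOCT counselling contact after Visit 1 with arm as the instrument. AOCT participants get lozenges at Visit 1 and M-UC participants get patches at theirs, whatever contact follows. Assignment would therefore change treatment even in people classed as not receiving it, which breaks the exclusion restriction.

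The cost is a little more analysis wording and the loss of an adherence-adjusted between-arm estimate. No new data are needed.

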*Primary Aim 2:* Another primary aim is to compare AOCT and M-UC on outcomes important to healthcare systems: net monetary benefit (NMB), incremental cost-effectiveness ratio (ICER), cost per long-term quit, and patient ratings of treatment and healthcare system quality. All of these will inform decision-making with regard to the efficient allocation of healthcare resources. Specifically, we hypothesize that, relative to M-UC, AOCT will produce an NMB higher than zero. Net monetary benefit analyses will convert the long-term relapse rates to Quality-Adjusted Life Years added (QALYs) and then monetize the QALYs added using a range of willingness to pay values. NMB analyses will allow us to compute confidence intervals and report whether these confidence intervals overlap for the AOCT relative to M-UC. For the ICER analyses, we will compare the additional cost of the AOCT to M-UC costs. Participants’ quality ratings will be analyzed using ANOVAs. We will examine the role of cessation success in satisfaction ratings and control for cessation success as needed.

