*Primary Aim 2:* Power analyses for the main systems outcome were computed based on the approach described by Glick and implemented in STATA Version 12.1 (StataCorp, College Station, TX) programs developed by Glick (<http://www.uphs.upenn.edu/dgimhsr/stat-samps.htm>). For purposes of powering cost-effectiveness comparisons, we utilized net monetary benefit (NMB) which has benefits over the incremental cost-effectiveness ratio (ICER). In contrast to a ratio measure such as the ICER, NMB is a continuous measure with a relatively normal distribution; in addition, the variance for NMB is well-defined which permits good estimation of confidence intervals, sample size, and power. NMB is computed as the difference in effectiveness ( $\Delta Q$ ) minus the difference in costs divided by willingness to pay ( $\Delta C/W$ ). Willingness to pay ( $W$ ) is conceptualized here as the amount society would be willing to pay for a health benefit; for our purposes,  $W$  is the amount that would result in an additional quality-adjusted life year (QALY). Power was computed for two key comparisons: (1) cost-effectiveness of COT relative to UC, and (2) cost-effectiveness of AOT relative to UC. We made the following assumptions for each of these comparisons: sample size of  $n=300$  for the Abstinence-Optimized Cessation Treatment and  $n=300$  for the Modern Usual Care treatment; two-tailed test;  $\alpha=.05$ ; standard deviation (SD) for costs=250; SD for effects (i.e., abstinence rates)=.42; correlation for the difference in costs and effects=.1; and maximum willingness to pay=\$50,000. For the AOCT vs. M-UC comparison, we set the difference in abstinence effects at .1 (i.e., a 10 percentage point difference; 20% vs. 30%) and a cost difference at \$1222 reflecting a UC cost of \$128 and AOCT cost of \$1350. Power for this comparison is .60. However, we do have sufficient power (.80) to determine cost-effectiveness if there is a 12 percentage point difference in abstinence rates. This analysis requires a larger abstinence difference to establish that it is cost-effective, as well as clinically effective, because of the large cost differential.

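### Cessation Study, Primary Aim 2: the NMB analysis is described as a check of whether confidence intervals overlap, and the plan does not tie it to the hypothesised and powered between-arm NMB difference

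*Combined protocol and SAP*

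**What the plan says.** Under Analytic Plans, Cessation Study, Primary Aim 2, NMB is listed among the outcomes of a primary aim. The stated hypothesis is that "relative to M-UC, AOCT will produce an NMB higher than zero". Quality-adjusted life years (QALYs) come from long-term relapse rates, and the plan will "monetize the QALYs added using a range of willingness to pay values". The only NMB comparison it then names is: "NMB analyses will allow us to compute confidence intervals and report whether these confidence intervals overlap for the AOCT relative to M-UC". It gives no interval level and does not mention zero. The ICER and ANOVA sentences that follow concern other outcomes.

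The power section for the same aim treats NMB as a between-arm quantity: "NMB is computed as the difference in effectiveness" less the cost difference divided by willingness to pay. It specifies a two-tailed test at alpha .05 and reports: "Power for this comparison is .60. However, we do have sufficient power (.80) to determine cost-effectiveness if there is a 12 percentage point difference".

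**The concern.** The hypothesis and the power calculation both concern one quantity, the NMB of AOCT minus that of M-UC, set against zero. The overlap sentence can be read as describing something else: one interval for each arm, inspected for overlap. Two arm-level 95% intervals can overlap while the 95% interval for their difference excludes zero, so the reported comparison could fail to show a difference that the powered test would declare.

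At stake is whether the analysis section states the comparison that answers this primary-aim hypothesis. As written, the analysis and power sections can be taken to point to different criteria, which leaves room to choose between them after the data are seen. The point concerns NMB only. It is separate from the .60 power at 10 points, which the plan already concedes.

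**Working it through.** **Inputs** (power section, Cessation Study, Primary Aim 2): 300 per arm; SD of effects .42; SD of costs $250; correlation .1; willingness to pay W = $50,000; cost difference $1,350 − $128 = $1,222; abstinence difference .10 or .12; two-tailed alpha .05.

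**Step 1: reproduce the plan's power.** In dollars, incremental NMB = W × (abstinence difference) − cost difference.

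- 10 points: 50,000 × .10 − 1,222 = $3,778
- 12 points: 50,000 × .12 − 1,222 = $4,778
- Per-person SD = √[(50,000 × .42)² + 250² − 2 × .1 × 21,000 × 250] = √440,012,500 = $20,976
- SE of the difference = 20,976 × √(2/300) = $1,713
- z = 3,778/1,713 = 2.206 and 4,778/1,713 = 2.790
- Power = Φ(z − 1.960) = .597 and .797

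These match the stated .60 and .80. A one-sided test gives .713 and .874, which do not match. Setting the correlation to 0 or −.1 changes the two-sided results by no more than about .002. The plan's figures are therefore those of a two-sided 5% test of the difference against zero.

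**Step 2: the per-arm overlap reading.** Assume equal arm SEs and intervals at a common level with normal quantile c. The intervals separate when the difference exceeds 2c × (arm SE). Since the SE of the difference is √2 × (arm SE), the critical value is c√2 SEs of the difference.

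| Interval level (assumed) | Critical value | Two-sided alpha | Power, 10 points | Power, 12 points |
|---|---|---|---|---|
| Difference test (plan's power section) | 1.960 | .050 | .597 | .797 |
| 83.4% per arm | 1.959 | .050 | .597 | .797 |
| 90% per arm | 2.326 | .020 | .452 | .679 |
| 95% per arm | 2.772 | .0056 | .286 | .507 |

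The power columns use Φ(z − critical value). A simulation of 20,000 replicates at the 95% level gave .285 and .503. If one arm's SE is twice the other's, the 95% critical value is 1.960 × 3/√5 = 2.630, with alpha .0085.

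**Step 3: an example in dollars.** With 95% intervals, the smallest observed difference that counts as positive is 1.960 × 1,713 ≈ $3,357 for the difference test and 2.772 × 1,713 ≈ $4,747 for non-overlap. If the observed difference equalled the 10-point planning value of $3,778, its 95% interval would be about $421 to $7,135. That excludes zero, yet the two arm intervals would overlap.

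**Side note: scale of the power figures.** The power section enters abstinence directly as the effect ("SD for effects (i.e., abstinence rates)=.42") and uses a "maximum willingness to pay" of $50,000, where willingness to pay "is the amount that would result in an additional quality-adjusted life year (QALY". With q QALYs per quit, incremental NMB is qW × (abstinence difference) − 1,222, and the SD also depends on q and W only through qW. So .60 and .80 apply wherever qW = $50,000. The documents give no q. For assumed products, power at 10 and 12 points is .32 and .55 at $25,000, and .73 and .88 at $100,000.

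**The case against.** The best defence is that the sentence was meant to ask whether the interval for the NMB difference overlaps zero. There is real support for this. The power section defines NMB only as a difference, and no arm-level NMB is defined anywhere. The overlap sentence repeats the relative-to-M-UC phrasing of the above-zero hypothesis. The plural intervals could be one per willingness-to-pay value, since a range of values is mentioned just before. On this reading there is loose wording and no wrong method. This stands as a possible reading, but the sentence never mentions zero, so the text does not settle the matter.

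Second, the sentence says what will be reported, not what will decide the conclusion, and the power section does contain a test. That also stands. A reader might infer that the trial will judge cost-effectiveness by overlap and that its power is really .29 or .51. The documents do not support that: those figures need the per-arm reading, an assumed 95% level, and overlap used as the decision rule.

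A reader might also infer that overlap can never produce a false claim of benefit. That fails for intervals below about 83.4%: two 80% intervals give a critical value of 1.81 and alpha of about .07. Because the plan gives no level, the error can be called conservative only at conventional levels such as 90% or 95%.

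**Conclusion.** The point holds as a clarification that should be made. The only NMB comparison named in the analysis section is ambiguous, and on one reading that its words allow, it matches neither the hypothesis nor the powered test. On that reading, with equal SEs and 95% intervals, the threshold rises from 1.96 to 2.77 SEs of the difference. If overlap were used to conclude, power on the plan's own inputs would be about .29 and .51 instead of .60 and .80. These power figures belong to the power section's abstinence-scale inputs and do not carry over to a QALY-based NMB with a different qW.

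Two stronger inferences are not supported. The plan's .60 and .80 are not wrong, and they are not confined to one QALY per quit: two QALYs per quit at $25,000 gives the same product and the same power. Nor is it a defect to report NMB over a range of willingness-to-pay values. Naming a single primary value would be a preference.

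**What to change.** Replace the overlap sentence in Analytic Plans, Cessation Study, Primary Aim 2 with:

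> We will estimate the incremental NMB (AOCT minus M-UC) with a two-sided 95% CI at each willingness-to-pay value, and conclude that AOCT has a positive NMB at a given value if the CI lies above zero.

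This serves either intended meaning. It brings the analysis into line with the stated hypothesis and with the two-sided 5% test behind .60 and .80. The cost is one sentence, with no additional data, participants or assessments. It does not raise the power of .60 at 10 points.

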**Cessation Study**

This study will enroll at least 600 participants to address the primary aims.

*Primary Aim 1:* We computed power for the GLMM longitudinal analysis of abstinence outcomes using a SAS macro developed by Dang and colleagues with the following parameters:  $N=300$  per group; 3 time-points; drop-out rate of 20%; treatment marginal rates (over time) of 30% vs 40%; random effects variance=1; and within-subject correlation=0.6. Power for this scenario is 0.91. Thus, the proposed study appears to be powered adequately to yield a statistically significant group difference in point-prevalence abstinence in the longitudinal GLMM analyses.

“Breaking Addiction to Tobacco for Health (BREATHE) Study”

PI: [name], MPH, MBA; UW-CTRI Center Grant: 1P01CA180945-01.

Power analyses were also computed for 6-month point-prevalence abstinence using nQuery Version 7.0 (Statistical Solutions, Cork, Ireland). With sample sizes of Abstinence-Optimized Cessation Treatment=300, and Modern Usual Care=300 we examined the power to detect the primary outcome—biochemically confirmed 7-day point-prevalence abstinence at 6 months post-target quit day. A previous meta-analysis found that abstinence rates at 6 months post-quit were 23.4% of participants receiving 8 weeks of nicotine patch and 28.1% for those receiving quitline counseling and medication, as will occur in the M-UC treatment. Given that this will be an effectiveness trial with only 1 quitline call, we expect that M-UC will likely produce a lower 6-month abstinence rate of approximately 20%. With  $\alpha=.05$ , and  $n=300$  for M-UC and  $n=300$  for the AOCT, we are powered at .80 to detect a 10% difference in relapse rates of the AOCT vs. M-UC. Therefore, we are powered to detect approximately a 10% treatment effect, which we consider to be clinically meaningful.

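### The Primary Aim 2 comparison of patient ratings may be adjusted for cessation success, a post-randomization outcome, with no stated trigger and no statement of which result is primary

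*Combined protocol and SAP*

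**What the plan says.** Under Analytic Plans, Cessation Study, Primary Aim 2, the outcomes important to healthcare systems include net monetary benefit (NMB), the incremental cost-effectiveness ratio, "cost per long-term quit, and patient ratings of treatment and healthcare system quality". The model for the last of these is brief: "quality ratings will be analyzed using ANOVAs". The next sentence reads: "We will examine the role of cessation success in satisfaction ratings and control for cessation success as needed". No trigger is defined, no cessation measure or time point is named, and the adjusted analysis carries no secondary or supplementary label.

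Primary Aim 1 of the same study states that "we hypothesize that participants receiving AOCT will have higher cessation rates at each timepoint than those receiving M-UC".

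Two other parts of Analytic Plans deal with comparable adjustments and do label them. Under Cessation Study, Primary Aim 1, models that control for treatment adherence are placed among the secondary analyses. Under Long-term Quitting Study, Primary Aim, the main model leaves out the later-stage Relapse Recovery (RR) Cessation factors, which appear as covariates only in supplementary analyses.

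**The concern.** Cessation success is measured after randomization, and the trial expects treatment to change it. Putting such a variable in the model changes what is estimated. Without it, the arm difference is the total effect on ratings of being assigned to AOCT. With it, the estimate approaches a direct effect net of quitting, and equals one only under further assumptions, chiefly that quitting and ratings share no unmeasured causes. Motivation or rapport with the counselor could plausibly be such a cause.

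The second difficulty is the words *as needed*. They follow a promise to examine how cessation relates to ratings, so the decision to adjust comes after the data are seen. If the two models disagree, the plan does not say which one answers Aim 2. Health systems are the stated audience for this aim, and the total effect of offering AOCT is the natural quantity for them.

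**Working it through.** **Inputs from the documents** (Power for Primary Outcomes, Cessation Study)
- Arm sizes: "With sample sizes of Abstinence-Optimized Cessation Treatment=300, and Modern Usual Care=300".
- Control abstinence: "we expect that M-UC will likely produce a lower 6-month abstinence rate of approximately 20" percent.
- Arm difference: "a 10 percentage point difference; 20% vs. 30" percent.
- α = .05. The NMB calculation is stated as a "two-tailed test"; two-sided testing is assumed for abstinence.

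**Inputs not in the documents.** No rating SD, no rating effect size and no link between quitting and ratings is given. Assumed for illustration: quitting raises the rating by g = 0.25 to 1.0 SD, and the direct effect of AOCT is d = 0 to 0.3 SD.

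**Step 1. Reproduce the plan's figures.** These check the assumed difference in the covariate and the NMB inputs; the plan has no figure for ratings.
- Abstinence, 20% vs 30%, 300 per arm, pooled variance: (0.10 − 1.96 × √(2 × 0.25 × 0.75/300)) / √((0.16 + 0.21)/300) = (0.10 − 0.0693)/0.0351 = 0.874, so power is 0.81 (stated .80).
- NMB: SE² = 2 × (250² + (50,000 × 0.42)² − 2 × 50,000 × 0.1 × 250 × 0.42)/300, so SE ≈ 1,713. At 10 points, (5,000 − 1,222)/1,713 − 1.96 = 0.246, power 0.60 (stated .60). At 12 points, power is 0.80 (stated .80).

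Both reproduce, and neither uses the ratings.

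**Step 2. What adjustment removes.** Total effect = d + (0.30 − 0.20) × g. Adjustment removes the second term. Its share of the total is 0.10g/(d + 0.10g).

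| g (SD) | Removed (SD) | Share, d = 0.1 | Share, d = 0.2 | Share, d = 0.3 |
|---|---|---|---|---|
| 0.25 | 0.025 | 20% | 11% | 8% |
| 0.5 | 0.05 | 33% | 20% | 14% |
| 1.0 | 0.10 | 50% | 33% | 25% |

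If d = 0, the whole effect is removed.

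**Step 3. Scale.** With 300 per arm and no attrition, the standard error of a standardized difference is √(2/300) = 0.082 SD. A loss of 0.05 or 0.10 SD is about 0.6 or 1.2 standard errors. The difference detectable with 80% power is (1.96 + 0.84) × 0.082 ≈ 0.23 SD.

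**Step 4. Simulation.** Least squares, 300 per arm, 4,000 runs per row, effects in residual-SD units. The common cause, where present, is an unmeasured factor correlated 0.5 with the propensity to quit and raising ratings by 0.5 per SD.

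| Assumed truth | Estimate, unadjusted / adjusted | Rejects, unadjusted / adjusted | Either rejects |
|---|---|---|---|
| d = 0.2, g = 0.5, no common cause | 0.25 / 0.20 | 85% / 68% | 85% |
| d = 0.2, g = 0.5, common cause | 0.25 / 0.16 | 74% / 41% | 74% |
| d = 0, g = 0, no common cause | 0.00 / 0.00 | 5.2% / 4.9% | 5.6% |
| d = 0, g = 0, common cause | 0.00 / −0.04 | 5.1% / 7.3% | 9.1% |

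In the second row the adjusted estimate falls below even the direct effect of 0.2. The bias is negative here because the assumed factor pushes quitting and ratings the same way; a factor pushing them opposite ways would reverse the sign. One reading of *as needed* is to adjust whenever cessation significantly predicts ratings. Under the inputs of rows 1, 2 and 4, that rule rejects as often as the adjusted model does (68%, 41% and 7.3%).

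**The case against.** The strongest reply is that the plan commits first to ANOVA. In the power section for the Clinic Randomized Control Trial, the authors separate ANOVA from ANCOVA and assign covariates to the latter. On that reading the unadjusted arm comparison comes first, and cessation success is then explored as an explanation. A reader might infer that the adjusted model replaces the ANOVA, so that the ratings comparison is no longer randomized. The documents do not say that. What remains is narrower: nothing says the adjusted model does *not* supply the Aim 2 result, whereas adherence and the RR Cessation factors are explicitly kept out of the main analyses.

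The second reply concerns timing. Table 12, the Cessation Study schedule, has no row for treatment or healthcare-system ratings. The common assessment paragraph under Data Collection describes the ratings without a time. In the Motivation Study (Table 11), healthcare system evaluation is collected at Visit 1 and Weeks 12 and 39, and treatment acceptability at Week 52, so timing can differ by rating. Later cessation cannot mediate a rating taken before the quit attempt. This reply stands: loss of treatment effect through quitting is conditional on timing. It does not rescue the undefined trigger.

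The third reply is that the stakes are modest. The only hypothesis stated under Aim 2 concerns NMB, which is also the only Aim 2 outcome with a power figure. That is correct and limits the weight of the point.

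**Conclusion.** The point holds in a limited form. The plan permits a primary-aim comparison to be adjusted for an outcome that treatment is expected to change, at a time and by a rule left open. For ratings taken after the quit attempt, and if quitting affects ratings, the loss is 0.10 × g SD, or 0.025 to 0.10 SD over the assumed range of g. The 0.10 is the plan's own abstinence difference; g is an assumption. Shared causes of quitting and ratings would add bias whose sign the documents cannot settle. There is no distortion if quitting neither affects ratings nor shares causes with them, or if treatment does not change quitting.

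Two stronger inferences are not supported. The 9.1% rejection rate is not the error rate of this plan: it needs an assumed common cause and reporting of whichever model is significant, and without the common cause it is 5.6%. Nor does the point reach the trial's main conclusions: the abstinence and NMB analyses do not depend on this sentence, and no stated figure is wrong. This is a minor but worthwhile correction.

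**What to change.** In Analytic Plans, Cessation Study, Primary Aim 2, replace the sentence on controlling for cessation success with one to this effect:

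> *The Aim 2 result for patient ratings is the AOCT vs M-UC ANOVA with no post-randomization covariates; any model that includes cessation success is a supplementary or mediation analysis, using [named cessation measure] and ratings at [named time point].*

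If baseline covariates are wanted in the ANOVA, name them there, so that no further choice of model is left open. The investigators keep the analysis of how quitting relates to satisfaction, under a label that matches how the plan already treats adherence and the RR Cessation factors.

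The cost is one sentence in the plan. Sample size and stated power do not change, and the analysis fix requires no new data collection.
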